5.0 SUBJECTS

5.1 Source/Description of Study Group

All subjects who successfully complete Study #999a and any additional dosing during a continuation of that protocol, if applicable, are eligible to enter the #999a Extension protocol. All subjects who participate in this extension will be required to sign a new consent form.

5.2 Inclusion Criteria

Successful completion of the parent protocol (#999a) and any applicable continuation of that protocol without interruption of study participation.

5.3 Exclusion Criteria

No additional exclusionary criteria specific for this extension study are identified.

5.4 Termination Criteria

The termination criteria in this amendment are modified to permit longer absences from the study than in the parent protocol (see pages 11-12).

5.5 Concurrent Medication

Any concomitant medications used by the subject, including over-the-counter preparations, shall be recorded monthly on Form 05 in this Extension protocol.

6.0 DRUG INFORMATION

6.1 Formulation

See Drug Handling Protocol section of Protocol #999a.

Packaging/Storage Information

See Drug Handling Protocol section of Protocol #999a.

For the extension phase, the buprenorphine doses will be in the same prepackaged unit dose formulations as in the parent protocol, consisting of 1 ml liquid containing 1, 2, 4, 8, 12, 16, or 32 mg of buprenorphine.

Subjects in the Extension Protocol will not have individual dose therapy kits as they have in the parent protocol. Rather, each site will have a 36-drawer drug cabinet that will contain the study drug (see Appendix A - Drug Handling Protocol for more details).

In addition, each subject will have a dosing schedule that will specify:

- 1. which coded drug he/she should receive on Mondays through Thursdays or Mondays through Fridays-depending upon whether the clinic is operating on a 5 or 6 day study regimen, respectively
- 2. which coded drug should be received on Fridays or Saturdays.

Each time a subject is required to have a dose adjustment, the Pharmacy Coordinating Center (PCC), Albuquerque must be notified by [contact]). PCC will FAX a dose assignment to the site so the subject can be dosed without delay. To accomplish this, PCC requires one day's notice to implement this change in dose. (See Appendix A - Drug Handling Protocol, for more details.)

Labeling

See Drug Handling Protocol section of Protocol #999a.

Preparation of Drug for Administration

See Drug Handling Protocol section of Protocol #999a.

Stability

See Drug Handling Protocol section of Protocol #999a.

7.0 STUDY EXECUTION

7.1 Treatment

Number of subjects:

All subjects at each of 12 centers who have been receiving buprenorphine continuously and successfully completed parent protocol (#999a) and any applicable continuation.

Subject replacement/addition:

None

Premature Withdrawals:

If a subject either leaves the study voluntarily prior to completion or is terminated by the staff, the circumstances, if known, will be documented in the subject's study record and recorded on Form 08. In addition, PCC will be notified by each site when a subject is terminated.

Method of drug administration:

Medications will be administered by dispensing personnel, exactly as in the parent protocol. All staff at participating sites will remain blind to the subjects' doses except as discussed previously. As in the parent protocol, subjects will hold the medication under their tongue for 5 minutes following the sublingual dosage to assure maximal absorption.

Dose Schedule:

The number of dosing adjustments will be at the investigators' discretion, but each time a dosing change is made, the reason must be fully documented in the case report form. The doses available are: 1, 2, 4, 8, 16, and 32 mg. (A 12 mg dose also is available, but this dose only occurs in the reinduction and taper paradigms and is not a maintenance dose.) The highest maintenance dose available is 32 mg and the lowest is 1 mg.

As in the parent protocol, no take home doses will be allowed. Subjects must attend the clinic either Monday through Friday or Monday through Saturday, depending upon at which site the subject is enrolled.

The following sites will operate on a Monday through Friday schedule:

Hines VA
Boston VAOPC
New York VA

San Juan VA
San Francisco General
San Francisco VA

Those operating on a Monday through Saturday schedule are:

Milwaukee County Medical Complex West Haven VA Philadelphia VA

Subjects will receive a double dose of their study medication on either Fridays or Saturdays to eliminate the need for a Saturday and Sunday or a Sunday clinic visit, respectively. This is expected to "hold" the subject until Monday, but the results of this study will be more definitive in this regard.

Even though double doses are administered on Fridays or Saturdays, subjects who regularly are on 32 mg will still receive 32 mg on that day. This dose is assumed to be high enough that it will hold the subject for 70 hours or more (Walsh, et al, 1992b). Only 1 vial of medication will be given to a subject at any one time. Even on Saturdays, the double dose will be incorporated into the one unit dose vial assigned to the subject.

In order to assure the safety of individuals receiving dose increments either for weekend dosing or for dose escalations, the following procedures must be available at sites participating in this extension protocol:

- 1. Initiation of weekend doses for the first time in any given patient must occur during a period when the clinic has weekend "on call" medical staff available for or is open seven days per week with medical staff available for consultation during the weekend.
- 2. Increased doses, other than that described in #1 above, should occur during Monday through Wednesday or Monday through Thursday, depending upon whether clinic is open 5 or 6 days a week, respectively, unless the clinic provides medical staff available for consultation throughout the week. In this case, limitations on dose increment scheduling are not required.

Dose Escalation/Reduction:

Subjects who successfully complete the 16-week parent protocol and applicable continuation dosing will be offered the opportunity to continue buprenorphine at their present dosage, or if necessary, at the investigator's discretion, have their present dose

either doubled (maximum 32 mg/day) or halved (minimum 1 mg/day) as discussed below. Double-blind dosing will be maintained (as described above).

Adjustment of Dose:

This amendment will allow for an adjustment of dosing, at the investigator's discretion. When a subject completes the parent protocol, the investigator may keep the subject on the same dose that he/she was on during the parent protocol, or the dose may be increased (doubled) or decreased (halved). Only one adjustment may be made at any one time, which is either twice or one half the current dose. There is no limit to the number of dose adjustments that may occur during the study extension, providing that only one adjustment is effected on any given day. Regardless, the protocol must still remain double blinded except as provided for above (see page 1).

Dose Assignment Schedule:

Up to one year including time spent in the Parent Protocol and applicable continuation dosing after the Parent Protocol.

Dependent upon a number of factors, further dosing with buprenorphine may be contemplated at the conclusion of this extension amendment. If offered, such dosing would be addressed in a subsequent protocol. If accessibility to buprenorphine for subjects in this study is either not feasible or not indicated, all appropriate medical options will be reviewed with subjects in this study prior to termination from this study.

Treatment Termination:

The investigator shall terminate a subject from participation in this study for any of the following reasons:

- 1. Medication toxicity, evidenced by significant signs or symptoms, that does not respond to halving the dose on repeated, successive occasions.
- 2. Missing 9 consecutive calendar days without study drug during the blinded portion of the extension. Once the study becomes unblinded, exceptions may be made for hospitalizations and excused absences as provided for in clinic policy.
- 3. Requiring a sixth reinduction in the extension protocol (i.e., subject has already been reinducted 5 times during the extension study for missing 4, 5, 6, 7, or 8 consecutive days of dosing).
- 4. Intercurrent illness or medical complications precluding safe administration of buprenorphine.
- 5. Administrative termination (e.g., moved from area, violence or threats of violence within clinic, excessive drinking or toxicity resulting from illicit drug abuse).
- 6. Pregnancy

7.2 Study Procedures

Psychosocial Services:

Psychosocial services are those given to the subject in addition to regular contact with staff for dosing, urine collection, or to complete the case report forms. NIDA encourages such support for this protocol, and recommends that formal counseling and other psychosocial services not be less than one hour/month. Reporting of these services to the sponsor is not required during this amendment.

Schedule of Events:

All measures will remain as they were in the parent protocol, except when noted (see section Clinical Observations, below).

7.3 Clinical Observations

Physical Exams/Vital Signs:

at 12 weeks, 24 weeks, 36 weeks, or whenever termination occurs

The physical exams, performed every third month, may be abbreviated on the clinical judgment of the on-site physician based on the subject's relative good health. More frequent and more thorough examinations will be performed as necessary.

Laboratory Tests: clinical blood chemistries (CBC, SMA-12) and routine

urinalyses: at 12 weeks, 24 weeks, 36 weeks, or whenever

termination occurs

Clinical Measurements: Self report of drug use: weekly

Electrocardiograms: will be performed at 24 weeks after the parent protocol is completed and at

termination

Concomitant medications will be recorded: monthly

Adverse Experiences including Reporting: see original protocol

Pharmacokinetic Measurements:

Although pharmacokinetic studies will not to be performed under this amendment, paired trough plasma samples will be collected whenever a change of dose is planned: a baseline trough sample will be collected just prior to the dose adjustment (and before the subject is actually dosed); and again two weeks thereafter, on the same day of the week as the baseline sample, if possible, another trough sample will be collected. This second trough sample should reflect steady state blood levels. The procedure for collecting steady state blood samples is listed as an amendment to the Parent #999a Protocol:

"Attempt to collect blood as soon as possible after the 14th day of dosing (day 15 would be ideal). Please note, however, that if the subject requires a reinduction during the first two weeks, the 14-day count should re-start with the 1st day of reinduction. Also, do not draw blood on the day after a dose has been missed. The subject must have received dosing for at least three consecutive days prior to drawing blood levels. It is conceivable, that in the case of subjects with many absences, the plasma levels might not be drawn until the fourth week or even later. Similarly, apply the same procedures for the eighth week sample."

"In occasional instances, it may be impossible to collect blood under the conditions and restrictions described above."

Plasma samples should also be collected whenever a significant or serious/unexpected adverse event occurs. These samples should be taken as closely as possible to the event in question.

PLEASE NOTE: Plasma samples will still be sent to the University of Utah.

Urine Collection for Drug Screen Analysis:

Because this is a safety study, urine drug screens will not be an outcome measure in the extension protocol as they were in the parent protocol. Consequently, the sponsor will not collect urine drug screen results. Individual sites are advised, however, to monitor drug usage by screening urine samples as per clinic policy at that site. It is expected that information gathered from the drug screen tests will be used by standard clinical practice to determine the potential utility of drug dosage modification, continued protocol participation, and for psychosocial counseling purposes.

8.0 CRITERIA FOR RESPONSE

Measures and Measuring Instruments:

Those variables used primarily to evaluate safety are:

- 1. Adverse experiences will be evaluated at the time of entry into the extension protocol and weekly thereafter as in the parent protocol.
- 2. Laboratory data CBC, UA, SMA-12 will be collected every twelve weeks and EKGs will be taken 24 weeks after the completion of the parent protocol and at the termination.

Those variables which will be used primarily to provide descriptive analyses of method modifications (dose adjustments, dosing schedule, doubled weekend doses) for inclusion in "directions for use" label language are:

- 1. Self reported frequency of illicit drug and ethanol use will be obtained every week.
- 2. Abbreviated self report including reports of opiate side effects and withdrawal symptoms.

9.0 STATISTICS

This extension is intended primarily to gather longer term safety data. Safety parameters to be analyzed both descriptively and as group and paired t-tests utilizing all data generated on participating patients are:

- 1. All safety parameters (adverse events, protocol discontinuation, laboratory studies)
- 2. Dose adjustment, dose schedule modification, and doubled weekend doses compared to parent protocol data for safety variables (#1 above)

Analysis of safety data will include both relevant data from the extension amendment period as well as the prior parent protocol and applicable continuation amendments. Thus, the period of analysis for all subjects will be for up to one year, or until the point of termination from the study.

Modifications of methods in this extension amendment will also permit consideration of data relevant to these modifications. These modifications are:

- 1. unblinding of the results of urine toxicology tests, allowing each site to perform its own drug screening to monitor illicit drug use
- 2. adjustment of dosage including a new 32 mg dose
- 3. reduction of clinic attendance to 5 or 6 days per week depending upon the decision of study site personnel
- 4. doubling of weekend dosage in place of take home dosages.

A descriptive analysis of these modifications relevant to safety and outcome will be completed, dependent in part of the number of patients who opt to modify their dose. This extension amendment provides data for the following analyses:

- 1. Percent patients experiencing opiate withdrawal including craving or side effects by dose and dosing pattern (5 or 6 day dosing)
- 2. Percent missed doses by day of the week and by dose level of buprenorphine.

All comparisons with the parent protocol will be made by displaying the measures graphically and by using simple t-tests. The comparisons with the parent protocol will be made using the data for all patients from the parent protocol as well as for only those patients who were allowed to enter the extension protocol. The latter comparison will enable us to evaluate the usefulness of the extension protocol for those patients who crossed over to the extension protocol.

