Local sites will have some variability in the amount of psychosocial services provided; however, all sites should include at least one session of AIDS education. Psychosocial services are those given in addition to regular contact with staff to complete the case report forms. In general, formal counseling and other psychosocial services should not exceed one hour per week and not be less than one hour/month.

If a patient requires further counseling for significant life-crisis problems (e.g., death, loss of job, divorce), the investigator may increase the amount of counseling at his/her discretion. This shall be well-documented.

Termination of Patients From the Study

Once a patient has been assigned a randomized number from Perry Point, he/she shall not be replaced if terminated early. Patients are in the study voluntarily and can terminate their participation at any time. In addition, the investigators shall terminate a patient's participation for any of the following reasons:

- 1. Medication Toxicity (e.g., excessive sedation).
- 2. Missing 7 consecutive days of dosing.
- 3. Buprenorphine toxicity, evidenced by significant signs or symptoms, that warrants drug dosing to be withheld on three successive occasions.
- 4. When a patient requires a fourth induction (i.e., patient has already been reinducted 3 times for missing 4, 5 or 6 sequential days of dosing).
- 5. Termination by clinic physician because of intercurrent illness or medical complications precluding safe administration of buprenorphine.
- 6. Administrative termination (e.g., moved from area, violence or threats of violence within clinic, excessive drinking).
- 7. Pregnancy.

DATA MANAGEMENT

The data management for NDA purposes will be done by the VA Cooperative Studies Program Coordinating Center at Perry Point, Maryland. At the study sites, data will be collected on triplet NCR forms supplied by the Data Coordinating Center at Perry Point. Completed Case Report Forms (CRF) for each patient will be retained at the study site until reviewed by an authorized study project monitor. The monitor will send one copy to the VA Cooperative Studies Program Coordinating Center at Perry Point; and one copy will be sent to the NIDA project director. All other Case Report Forms and source documents will be retained at the study site.

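### Extension section 9.0 tests discontinuation against the parent study, but the entrants-only test can only show worsening and the all-parent test cannot isolate the modifications

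*Combined protocol and SAP*

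**What the plan says.** Section 9.0 of the extension amendment says the safety parameters will be "analyzed both descriptively and as group and paired t-tests utilizing all data generated on participating patients". Item 1 of its list is "All safety parameters (adverse events, protocol discontinuation, laboratory studies"). Item 2 takes dose adjustment, the changed schedule and doubled weekend doses, "compared to parent protocol data for safety variables (#1 above"), so discontinuation is one of the variables compared across phases.

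The section closes by specifying two sets of parent data: all parent patients, "as well as for only those patients who were allowed to enter the extension protocol". It adds that the second set will allow the usefulness of the extension to be judged for those who crossed over.

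Three other places bear on this:

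- Extension section 5.2 makes the entry condition "Successful completion of the parent protocol (#999a) and any applicable continuation of that protocol without interruption of study participation".
- Extension section 5.4 says "The termination criteria in this amendment are modified to permit longer absences from the study than in the parent protocol".
- The parent protocol (Termination of Patients From the Study) ends participation for "Missing 7 consecutive days of dosing", or when a further induction is needed after three reinductions. Extension section 7.1 ends it for "Missing 9 consecutive calendar days without study drug during the blinded portion of the extension", with exceptions possible once unblinded, or at a sixth reinduction. The toxicity criterion also differs: doses withheld on three successive occasions in the parent, no response to repeated halving in the extension.

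**The concern.** Discontinuation is both an outcome in this comparison and the variable on which the extension cohort was selected. Nobody who discontinued the parent can enter the extension. A within-patient comparison therefore has a constant on one side, and a comparison with all parent patients contrasts everyone randomised with those who stayed.

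Section 9.0 has no common time window, no common event definition and no caveat for this variable. Yet it asks for t-tests and attaches an inference to the entrants-only version. At stake is whether a significant result on discontinuation, in either direction, would be taken as evidence about flexible dosing, fewer clinic days or doubled weekend doses.

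**Working it through.** The extension states no sample size, significance level or expected discontinuation rate, so there is no figure to reproduce.

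**Inputs from the documents**

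- Parent size: at least 480 (Method); 720 if every site fills (Participation).
- Parent dropout: 30% (simulation under Patient Screening, Recruitment, and Informed Consent); 60% to 80% (ARC 090, under Statistical Methods).
- Follow-up: 16 weeks in the parent; up to 52 − 16 = 36 weeks in the extension if there was no continuation.

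**Assumptions**

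- Two-sided .05.
- Every completer enters, giving 480 × 0.20 = 96 entrants at the low end and 720 × 0.70 = 504 at the high end.
- ARC 090 dropout is applied to 16 weeks as an illustration. That study ran 25 weeks, 17 of them maintenance.

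**1. Entrants-only comparison**

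Score discontinuation 0 or 1 in each phase. The parent score is 0 for every entrant, so the difference is 0 or +1. With *k* discontinuations among *n* entrants and p = k/n,

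t = p / √(p(1−p)/(n−1)) = √(k(n−1)/(n−k)).

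- n = 96, k = 4 (4.2%): √(4 × 95/92) = 2.03, p = .045.
- n = 504, k = 4 (0.8%): √(4 × 503/500) = 2.01, p = .045.

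Four is the smallest number reaching p<.05 at each of the six entrant counts tried (96, 144, 192, 288, 336, 504). With no discontinuations there is no difference to test. No outcome favours the extension.

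**2. All-parent comparison, unequal follow-up alone**

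If the weekly hazard is the same in both phases, parent dropout *d* over 16 weeks becomes 1 − (1−d)^(36/16) over 36 weeks:

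- d = 30% gives 55%.
- d = 60% gives 87%.
- d = 80% gives 97%.

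On cumulative proportions the extension then looks worse. It looks better only if its weekly hazard is below 16/36 = 0.44 of the parent's.

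**3. All-parent comparison, adding completer selection**

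Let individual hazards vary (gamma frailty, variance *v*, an assumption) and stay unchanged by the extension. Then S(H) = (1+vH)^(−1/v) and H16 = ((1−d)^(−v) − 1)/v. Extension dropout is 1 − S(H16 × 52/16)/S(H16) over 36 weeks, and 1 − S(2 × H16)/S(H16) over its first 16. The limit v = 0 is the exponential case in step 2.

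| Parent, 16 weeks | Extension, 36 weeks: v = 0 / 1 / 4 | Extension, first 16 weeks: v = 0 / 1 / 4 |
|---|---|---|
| 30% | 55.2 / 40.3 / 22.1% | 30.0 / 23.1 / 13.2% |
| 60% | 87.3 / 57.4 / 25.2% | 60.0 / 37.5 / 15.6% |
| 80% | 97.3 / 64.3 / 25.5% | 80.0 / 44.4 / 15.9% |

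Nothing about treatment changes in this table. Over 36 weeks the extension can still look worse (55.2% or 40.3% against 30%) or better (22.1% against 30%). Over equal windows it looks better whenever patients differ in their hazard. The differing termination rules come on top of this.

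**The case against.** The extension is mainly a descriptive safety study. Section 9.0 sets no significance level, hypothesis or decision rule, and section 1.0 says the dosing experience will be characterised descriptively and is not efficacy data. Section 1.0 also plans aggregate methadone-clinic figures, including dropouts and terminations, as a separate comparator. This stands as a limit on how much the point matters. It does not remove it, because section 9.0 still asks for t-tests on discontinuation and says what the entrants-only comparison is for. The methadone figures do not alter either parent comparison.

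A reader might infer three stronger things that the documents do not support:

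- *Both comparisons are fixed by design, with the all-parent one bound to favour the extension.* It is not. Selection lowers extension discontinuation, while 36 weeks against 16 raises cumulative discontinuation. The net sign is open.
- *The extension's absence rule is simply looser.* Section 5.4 describes longer permitted absences, but the unit also changes. At a Monday-to-Friday site, a patient dosed on Friday who misses the next five visits reaches 9 calendar days without drug by the second Sunday, if scheduled days off count. The parent's 7 days, with daily dispensing, are 7 missed visits. The rules differ, and in missed visits the direction is not clear.
- *The directions-for-use labelling rests on this comparison.* Section 8.0 names the variables used primarily for that purpose: self-reported drug and ethanol use, and side effects and withdrawal symptoms. Discontinuation is not among them.

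**Conclusion.** The concern holds, with different force for the two comparisons.

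The entrants-only comparison of discontinuation is wrong as written. Its direction follows from the entry rule alone and needs no assumption. That four events suffice for nominal significance rests on a two-sided .05 level and on 96 to 504 entrants. The comparison cannot show usefulness for this variable.

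The all-parent comparison is confounded by completer selection, differing termination rules and unequal follow-up. Neither its sign nor its size is fixed, and it cannot be attributed to the modifications. The percentages in the working illustrate this and are not predictions; the frailty variances are assumptions.

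The point is confined to discontinuation. The entry rule does not set parent adverse-event or laboratory values to a constant, and those comparisons are not part of this finding. The consequence is moderate, since the extension is largely descriptive, but the correction is worth making before analysis.

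**What to change.** In section 9.0:

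1. Remove protocol discontinuation from the parent-versus-extension t-tests, and state that the entrants-only comparison of discontinuation will not be used as evidence of the extension's usefulness.
2. Report extension discontinuation descriptively by life table from extension entry, by dose, by 5- or 6-day schedule and by Form 08 reason, with blinded and open periods shown separately. Because doses may change repeatedly, state in advance which dose defines the groups.
3. If parent discontinuation is shown alongside, use equal time windows, no test, and a stated caveat on completer selection and differing termination rules.

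A common event such as a run of 7 or more undosed days should not be substituted. Seven consecutive missed days is itself a parent termination criterion, so parent completers would again score 0. Scheduled days off also count differently: at a 5-day site, a patient dosed on Friday who misses Monday to Friday has 7 undosed calendar days after 5 missed visits.

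The cost is a rewording and a little programming on data already collected. The sponsor loses a comparison that has no valid interpretation. No change to the clinical termination rules is proposed.
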